6.2 Treatment Study Period

6.2.1 Visit 1 (Day 1)

Subject will be presented the consent document prior to any procedures on this day. Between 7AM and 9AM, baseline labs, including morning cortisol, ACTH, and other steroid hormones and metabolites (5ml serum, 5ml EDTA) and a serum pregnancy test will be obtained. A comprehensive metabolic panel and complete blood count will be obtained if not already performed in the prior 3 months. Patients will be provided a single dose of 600mg mifepristone to be administered orally, and subjects will be instructed to take the drug between 10PM and 11PM on Day 1. If the participant is scheduled for an ITT as part of their medical care and is consented for this study prior to completing ITT, the study team will attempt to obtain left over blood samples for measurement of baseline labs relevant for

mifepristone testing, if the serum is drawn before 10AM, the lab draw that is part of Day 1 of the study could be omitted in this scenario.

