6.2.2 Follow-up

On Day 2, subjects will return to the clinic. It will be confirmed with the participants that they took mifepristone at the recommended time the previous night. We will obtain vital signs. Between 7AM and 9AM, repeat complete blood count (CBC), serum chemistry and hormone labs will be obtained. Adverse events will be collected.

On Day 7 and Day 30, participants will be contacted by phone to assess for any adverse events that occurred since Day 1.

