6.2.3 Subjects with history of adrenal insufficiency

Subjects with confirmed history of adrenal insufficiency (AI) on glucocorticoid replacement at baseline will be instructed on the following protocol for glucocorticoid dosing during testing. All components of the study protocol are otherwise the same as above.

- Day 0: Take the morning dose of glucocorticoid and hold the afternoon dose.
 - Day 1: Hold the morning dose until labs are drawn, then take the morning dose.
Hold the afternoon dose.
 - Day 2: Hold the morning dose until labs are drawn, then take the morning dose and resume baseline dosing schedule.
-
- Withholding afternoon doses of glucocorticoids for testing is routinely done in clinical practice and considered safe. Participants with diagnosed AI will be provided with a prescription for 4 mg of dexamethasone. Participants will be

provided with two 24-hour phone numbers to call if/when they experience any side effects. . Participants will be instructed to take 4mg of dexamethasone in case they experience significant signs of acute adrenal insufficiency [increasing nausea, lethargy, diarrhea, fever]. Participants are encouraged to contact one of the 24-hour phone numbers prior to taking the dexamethasone and are advised to call the number after taking the dexamethasone. As participants are scheduled for a blood draw the next morning they will be clinically assessed for adrenal insufficiency in case overnight concerns occur and further management will depend on this clinical evaluation. On day 2, participants with adrenal insufficiency will resume their usual dose of hydrocortisone replacement therapy and occurrence of adrenal insufficiency will become less likely. However, participants will remain advised to keep the dexamethasone emergency dosing and to contact the study team in case of any symptoms and signs of adrenal insufficiency

Table 1. Schedule of Activities

Protocol Activity	Screening Phone Call	Screening / Day 1^a	Day 2	Day 7 (+/- 3 days) Phone Call	Day 30 Phone Call (+/- 3 days)
Visit # / Phone call	1	1	2	3	4
Informed Consent		X			
Medical History	X	X			
Vitals Signs^b		X	X		
Serum Chemistry^c		X	X		
Complete Blood Count		X	X		
Pregnancy Test^d	X	X			
Hormone Labs^e		X	X		
Treatment with study agent (10 pm)		X			
Adverse Event Assessment		X	X	X	X

- a. There will be at least a one-week interval between ITT and mifepristone testing.

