The Principal Investigator must be notified within ONE business day of study team's knowledge of any event meeting the criteria and definition of a serious adverse event, regardless of attribution, occurring during the study or within 30 days of the last administration of the study related intervention.

The investigator must report all events meeting the criteria and definition of a serious adverse event as per the local IRB reporting requirements. Participants will be given contact information for study staff should they need to report any adverse events.

The Sponsor-Investigator will coordinate with the Michigan Institute for Clinical and Health Research (MICHHR) IND/IDE Assistance Program (MIAP) office for the reporting of any and all IND safety reports to the FDA as per the requirements outlined in 21 CFR312.32 which include all SAEs that are both unexpected and related to the intervention/treatment.

8.2.2 *Routine Reporting*

Lab results that are out of normal range but not clinically significant will not be reported. All other adverse events, such as those that are expected, or are unlikely or definitely not related to the study participation, are to be reported annually as part of regular data.

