12.2 Institutional Review Board (IRB)

Before implementing this study, the protocol, the proposed informed consent form and other information to be provided to subjects, must be reviewed by a properly constituted Institutional Review Board (IRB). Any amendments to the protocol must be reviewed and approved by IRBMED.

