12.3 Subject Information and Consent

The study team member will explain to each subject (or legally authorized representative) the nature of the study, its purpose, the procedures involved, the expected duration, the potential risks and benefits involved and any discomfort it may entail. Each subject will be informed that participation in the study is voluntary and that he/she may withdraw from the study at any time and that withdrawal of consent will not affect his/her subsequent medical treatment or relationship with the treating physician.

This informed consent will be given by means of a standard written statement, written in non-technical language. The subject should read and consider the statement before signing and dating it, and should be given a copy of the signed document. If the subject cannot read or sign the documents, oral presentation may be made or signature given by the subject's legally appointed representative, if witnessed by a person not involved in the study, mentioning that the patient could not read or sign the documents. No patient can enter the study before his/her informed consent has been obtained.

The informed consent form is considered to be part of the protocol, and will be submitted for IRB approval.

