12.4 STUDY DISCONTINUATION CRITERIA

12.4.1 *Stopping Rules for Safety reasons*

There will be no Data Safety Monitoring Board as this is a single site study.

However, we will continuously review SAE. If a study related SAE occurs in 3 of 6 patients or in >50% of patients at any time, the study will be terminated.

12.4.2 *Rules for Discontinuation of a Subject*

In the event a patient drops out of the study or is discontinued due to protocol violations, all attempts will be made to exit the patient in accordance with the protocol requirements.

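### The ±3-day tolerance on the final adverse-event call lets scheduled follow-up end before the 30-day serious adverse event period in section 8.2.1 closes

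*Combined protocol and SAP*

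**What the plan says.** Dosing: the study gives one 600 mg dose of mifepristone. Section 6.2.1 says "subjects will be instructed to take the drug between 10PM and 11PM on Day 1", so the last administration is the night of Day 1.

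SAE period: section 8.2.1 requires the principal investigator to be told, within one business day of the team learning of it, of any SAE "occurring during the study or within 30 days of the last administration of the study related intervention". This applies whatever the attribution.

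Follow-up: section 6.2.2 says "On Day 7 and Day 30, participants will be contacted by phone to assess for any adverse events that occurred since Day 1". Table 1 puts a tolerance of 3 days either side on both calls; the heading for the second is "Day 30 Phone Call (+/- 3 days"). Table 1 has no contact after that call.

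Other routes: section 8.2.1 adds "Participants will be given contact information for study staff should they need to report any adverse events". For participants with adrenal insufficiency, section 6.2.3 provides two 24-hour phone numbers and continuing advice to contact the team about symptoms. Section 12.4.1 says "However, we will continuously review SAE", without saying how a late event would come to light.

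**The concern.** The final call looks backward: it asks what has happened since Day 1. It can cover the 30-day period only if it is made after that period has ended. A tolerance on both sides does no harm at Day 7, because a later call picks up anything missed. At the last contact the minus side has no later call behind it.

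The notification duty starts when the team knows of an event. After an early final call, nothing on the schedule produces that knowledge for the remaining days. A participant who is in hospital, or who thinks an event has nothing to do with the study drug, may not ring, although section 8.2.1 covers events regardless of attribution. What is at stake is the completeness of SAE ascertainment in the last few days of a period that the protocol itself sets.

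**Working it through.** This is calendar arithmetic.

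**Inputs**
- Dose: Day 1, 10 to 11PM, once only (section 6.2.1).
- SAE period: 30 days from the last administration (section 8.2.1).
- Final call: Day 30 ± 3 days (Table 1).
- Earlier call: Day 7 ± 3 days (Table 1).

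**Permitted final-call days.** 30 − 3 = 27 to 30 + 3 = 33, which is 7 days.

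**When the period closes.** The protocol does not say how the 30 days are counted, so both counts are shown.
- Inclusive (dose day is day 1 of 30): 1 + 30 − 1 = Day 30, at the end of the day.
- Elapsed (30 full days after the dose): 1 + 30 = Day 31, at 10 to 11PM.

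**Shortfall = closing day − call day, in calendar days**

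| Call day | Inclusive count | Elapsed count |
|---|---|---|
| 27 | 3 | 4 |
| 28 | 2 | 3 |
| 29 | 1 | 2 |
| 30 | 0, but a daytime call precedes closure | 1 |
| 31 | covered | 0, but a daytime call precedes closure |
| 32 | covered | covered |
| 33 | covered | covered |

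Days 27, 28 and 29 are short on either count.

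**How many permitted days are early.** One rule is used here and in the fix: a daytime call on the closing day is early, because part of that day is still to come.
- Inclusive: Days 27 to 30, so 4 of 7.
- Elapsed: Days 27 to 31, so 5 of 7.

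In each case the last of these days is early by less than a day.

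**Largest shortfall.** A Day 27 call leaves 3/30 = 10% of the period (inclusive) or 4/30 = 13% (elapsed) without scheduled questioning. A call on the Day 30 target leaves less than a day (inclusive) or 1/30 = 3% plus part of a day (elapsed).

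**Effect of moving the window on the interval between calls.** The Day 7 call can fall on Days 4 to 10.
- Now: 27 − 10 = 17 to 33 − 4 = 29 days.
- Day 32 to 35: 32 − 10 = 22 to 35 − 4 = 31 days.
- Day 31 to 34: 31 − 10 = 21 to 34 − 4 = 30 days.

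**The case against.** The strongest reply is that no rule is broken. Section 8.2.1 says what must be notified and how fast once the team knows of it; it does not promise active questioning up to the last hour of the 30 days. That is right. A reader might infer that Table 1 and section 8.2.1 contradict each other, or that an SAE after an early call need not be notified. The documents support neither: an event that reaches the team after the call but occurred within the 30 days is still notifiable.

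The second reply is that the gap is already mitigated. All participants receive staff contact details, section 6.2.3 adds two 24-hour numbers, and section 6.2.2 aims the call at Day 30 itself. This also stands, and it is why the gap is small. It does not close the gap, because these routes rely on the participant making contact.

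The third reply is that little drug remains by then. Section 5.3 gives a mean (SD) half-life of 85 (61) hours after multiple dosing. Applied to a single dose and to parent drug only (an assumption), a 10AM call on Day 27 comes 25.5 × 24 = 612 hours after a 10PM dose. That is 612/85 = 7.2 half-lives, with under 1% remaining. At one SD above the mean (146 hours) it is 612/146 = 4.2 half-lives, with roughly 5% remaining. This lowers the chance that a missed SAE is drug related. It does not remove the gap, because the protocol chose 30 days regardless of attribution.

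The fourth reply is that a later final call delays questioning about everything since the Day 7 call. This is a real cost and is counted in the fix.

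**Conclusion.** The point holds as a minor ascertainment gap. On either day count, a compliant call on Day 27, 28 or 29 ends scheduled SAE questioning before the protocol's own 30-day period closes, by 1 to 3 calendar days (inclusive) or 2 to 4 (elapsed). If calls are made in the daytime, 4 of 7 or 5 of 7 permitted days are early to some degree.

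No average shortfall is given, because the documents do not say how calls will be spread over the window.

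A reader might infer that the safety stopping rule is compromised. The documents do not support that. Section 12.4.1 stops the study for study-related SAEs in 3 of 6 patients or in more than 50% of patients, and a few days without a scheduled call at the end of follow-up are unlikely to alter such a count. The recruitment endpoint and the cortisol analyses do not depend on the final call at all.

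**What to change.** Make the final-call window one-sided and open it after the SAE period has closed: Day 32 to Day 35, which works on either count. Change the column heading in Table 1 and the matching Day 30 wording in section 6.2.2. If the team prefers an earlier call, it can state in section 8.2.1 that the dose day is day 1; Day 31 to Day 34 is then enough.

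Costs:
- A minor protocol amendment. Section 12.2 says "Any amendments to the protocol must be reviewed and approved by IRBMED".
- Possibly a consent-form edit. Section 12.3 says "The informed consent form is considered to be part of the protocol", so the form must match if it names the call day. It is not among the documents reviewed.
- Later questioning. With Day 32 to 35 the interval between the two calls becomes 22 to 31 days instead of 17 to 29, so events in between are asked about somewhat later. The window opens 32 − 27 = 5 days later and closes 35 − 33 = 2 days later than now.
- A narrower window: 4 permitted days instead of 7.

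No extra contact or staff is needed. The gain is small, so the edit could reasonably wait and be combined with another amendment.

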7 ASSESSMENTS

7.1 Primary Endpoint Assessments

The primary endpoint of this pilot feasibility study is the rate of actual study participant recruitment. Reaching the target recruitment rate of one patient per 6 weeks over a 36-month period will be regarded as successfully in reaching the primary endpoint.

7.2 Secondary Assessments

The secondary endpoint is the correlation between cortisol measured after mifepristone administration and the peak cortisol measured in ITT. The results of the ITT will be regarded as the gold standard in diagnosis of diagnosis of secondary adrenal insufficiency. We expect that this correlation, as measured with the Pearson correlation coefficient (r) will be > 0.7 . As the true cut-off for diagnosis of adrenal insufficiency using post-mifepristone cortisol is unknown, we will analyze the data using ROC c-statistics for different cut-offs.

7.3 Exploratory Assessments

Exploratory endpoints include the impact of mifepristone on ACTH and other steroid hormones and metabolites, such as but not limited to corticosterone, aldosterone, androstenedione, 11-deoxycortisol, 11-deoxycorticosterone, DHEAS, DHEA, 17-hydroxyprogesterone, 17-hydroxypregnenolone. Analyses will be completed with c-statistics as well.

8 ADVERSE EVENT REPORTING

8.1 Adverse Event Definition

An adverse event (AE) is any untoward medical occurrence in a subject participating in an investigational study or protocol regardless of causality assessment. An adverse event can be an unfavorable and unintended sign (including an abnormal laboratory finding), symptom, syndrome or disease associated with or occurring during the use of an investigational product whether or not considered related to the investigational product.

These events may be:

- a. *Definitely related*: clearly associated with study drug/treatment
- b. *Probably related*: likely associated with study drug/treatment
- c. *Possibly related*: may be associated with study drug or other treatment
- d. *Unlikely to be related*, or
- e. *Definitely not related* to the study drug/treatment

For reporting purposes, an AE should be regarded as definitely or probably related to the regimen if the investigator believes that at least one of following criteria are met:

- a. There is a clinically plausible time sequence between onset of the AE and the administration of the study drug or treatment.
- b. There is a biologically plausible mechanism for the study drug or treatment causing or contributing to the AE.
- c. The AE cannot be attributed solely to concurrent/underlying illness, other drugs, or procedures.
- d. A potential alternative cause does not exist.

Serious Adverse Events (SAE): An adverse drug experience occurring at any dose that results in any of the following outcomes:

- a. Death
- b. A life-threatening adverse drug experience
- c. Inpatient hospitalization or prolongation of existing hospitalization
- d. A persistent or significant disability &/or incapacity
- e. A congenital anomaly or birth defect

Important medical events that may not result in death, be life-threatening, or require hospitalization may be considered a serious adverse drug experience when, based upon appropriate medical judgment, they may jeopardize the patient or subject and may require medical or surgical intervention to prevent one of the outcomes listed in this definition. A serious adverse experience includes any experience that is fatal or immediately life threatening, results in a persistent or significant disability/incapacity, requires or prolongs in-patient hospitalization, or is a congenital anomaly, cancer, or overdose.

Other important medical events that may not result in death, not be life-threatening, or not require hospitalization may be considered a serious adverse experience when, based upon appropriate medical judgment, the event may jeopardize the subject/patient and may require medical or surgical intervention to prevent one of the outcomes listed previously.

Expected adverse events are those adverse events that are listed in the protocol, the drug label, the Investigator's Brochure (version 18, June 2017), published literature, or in the study informed consent document.

Unexpected adverse events are those that:

- a. are not described in the Investigator's Brochure or drug label as far as drug is concerned.
- b. are not anticipated in the study informed consent. This includes adverse events for which the specificity or severity is not consistent with the description in the informed consent.

Unanticipated problem: Per FDA Procedural Guidance for Clinical Investigators, Sponsors, and IRBs (January 2009), A serious problem that has implications for the conduct of the study (requiring a significant and usually safety-related, change in the protocol such as revising inclusion/exclusion criteria or including a new monitoring requirement, informed consent or investigator's brochure).

Unanticipated problem Reporting: Per 21 CFR 312.66, 312.53 (c)(1)(vii), and 56.108(b)(1), should an Unanticipated problem occur during the investigation, the investigator will promptly report all unanticipated problems involving risks to human subjects or others to IRBMED /FDA.

The severity or grade of an adverse event may be measured using the following definitions:

Mild: Noticeable to the subject, but does not interfere with subject's expected daily activities, usually does not require additional therapy or intervention, dose reduction, or discontinuation of the study.

Moderate: Interferes with the subject's expected daily activities, may require some additional therapy or intervention but does not require discontinuation of the study.

Severe: Extremely limits the subject's daily activities and may require discontinuation of study therapy, and/or additional treatment or intervention to resolve.

8.2 Event reporting:

The study will comply with the IRB & FDA reporting requirements and guidelines.

8.2.1 *Serious Adverse Event Reporting Guidelines*

The Principal Investigator must be notified within ONE business day of study team's knowledge of any event meeting the criteria and definition of a serious adverse event, regardless of attribution, occurring during the study or within 30 days of the last administration of the study related intervention.

The investigator must report all events meeting the criteria and definition of a serious adverse event as per the local IRB reporting requirements. Participants will be given contact information for study staff should they need to report any adverse events.

The Sponsor-Investigator will coordinate with the Michigan Institute for Clinical and Health Research (MICHHR) IND/IDE Assistance Program (MIAP) office for the reporting of any and all IND safety reports to the FDA as per the requirements outlined in 21 CFR312.32 which include all SAEs that are both unexpected and related to the intervention/treatment.

8.2.2 *Routine Reporting*

Lab results that are out of normal range but not clinically significant will not be reported. All other adverse events, such as those that are expected, or are unlikely or definitely not related to the study participation, are to be reported annually as part of regular data.

9 DATA ANALYSIS/STATISTICAL METHODS

9.1 Sample Size Determination

This is a pilot-feasibility study with the primary endpoint of enrollment per month over a 36-month period. This study time frame was chosen due to the lack of any prior data regarding feasibility. Data required from this study will inform the planning of a post-pilot study.

9.2 Data Analysis

9.2.1 *Analysis Populations*

As the primary endpoint recruitment will be analyzed as a primary endpoint. The cortisol response with mifepristone administration will be compared with the maximal ITT cortisol level in all patients as a secondary endpoint. In addition, the hormone levels of participants with normal ITT will be compared to those with confirmed diagnosis of central adrenal insufficiency. Data from this study will inform planning of a larger post-pilot study.

9.2.2 *Analysis of Primary Endpoint*

The primary endpoint of this pilot feasibility study is actual study participant recruitment. Reaching the target recruitment of one participant every 6 weeks over a 36-month period (target n=26) will be regarded successful in reaching the primary endpoint. We estimate an enrollment of 90% of patients in this study. This is in accordance with our prior experience in patients with rare diseases, who are often motivated regarding study participation. We estimate a total of 85% of patients with complete data as we only anticipate minimal study drop out due to side effects of the drug or non-analyzable specimens. Study recruitment will be plotted over time and actual and target recruitment will be visually compared. We will regard a total of 22 patients as a target in meeting the primary endpoint.

9.2.3 *Analysis of Secondary Endpoints*

The secondary data point is day 2 cortisol and ACTH response to mifepristone administration. The day 2 cortisol level will be compared to the maximal ITT cortisol level to determine if and to what degree there is a correlation between the two measurements. In addition, a receiver operating characteristic (ROC) curve will be created with the day 2 cortisol level as the variable, and the ITT result as the “gold standard” test for adrenal insufficiency, to analyze the performance of cortisol as a diagnostic test. The cortisol and ACTH values in participants with normal ITT will be compared to those with confirmed diagnosis of central adrenal insufficiency, using a

t-test to determine whether there is statistically significant difference between the two populations.

9.2.4 *Analysis of Secondary Endpoints*

The secondary end points are levels of ACTH, other (than cortisol) steroid hormones and metabolites. These hormone levels will also be analyzed with t-tests to determine whether there is a statistically significant difference between participants with normal ITT and those with confirmed diagnosis of central adrenal insufficiency.

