12.4 STUDY DISCONTINUATION CRITERIA34
12.4.1 STOPPING RULES FOR SAFETY REASONS34
12.4.2 RULES FOR DISCONTINUATION OF A SUBJECT34
13 REFERENCES35

List of Tables

Table 1. Schedule of Activities.....22

PROTOCOL SYNOPSIS

Financial Sponsor: Corcept Therapeutics, Inc.
Name of Finished Product: Mifepristone (Korlym)
Study Title: Mifepristone Dynamic Testing for Diagnosis for Central Adrenal Insufficiency
Study Phase: Phase II
Primary Objective: Phase I of the study is to determine whether recruitment at our institution is sufficient for a study for mifepristone use as a diagnostic tool to diagnose central adrenal insufficiency and to generate data to inform a post-pilot study. Phase II of the study involves taking those recruited and having them complete the study to generate the data.
Study Design: Single-center pilot feasibility study of mifepristone to evaluate the recruitment of participants with the diagnosis of confirmed or suspected secondary adrenal insufficiency. Cortisol (secondary endpoint), ACTH and other steroid responses (exploratory endpoints) to mifepristone in participants with normal insulin tolerance testing (ITT) and participants with confirmed or suspected adrenal insufficiency will be analyzed. The study will test primarily for feasibility of recruitment (phase 1) and provide preliminary data for planning a post-pilot study (phase 2).
Study Population: Subjects with normal ITT and subjects with confirmed or suspected diagnosis of central adrenal insufficiency.
1. Criteria for Inclusion and Exclusion: Please see section 4.
Test Product; Dose; and Mode of Administration: Single dose of mifepristone 600mg, administered orally
Reference or Placebo Therapy; Dose; and Mode of Administration: None
Duration of Treatment: One day
Variables: Cortisol, ACTH

Statistical Methods:

- For the primary endpoint of recruitment actual recruitment will be compared to target recruitment (1 patient per 6 weeks). Actual and target recruitment per month will be plotted and visually compared. Recruitment of ≥ 26 participants and study completion and complete data on ≥ 22 patients will be a success regarding the primary endpoint.
- For the secondary endpoint the day 2 cortisol level will be compared to the maximal ITT cortisol level to determine if and to what degree there is a correlation between the two measurements.

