2.2 Endpoints

2.2.1 Primary Endpoint

The primary endpoint of this pilot feasibility study is actual study participant recruitment. Reaching the target recruitment rate of one patient every 6 weeks over a 36-month period will be regarded as successful in reaching the primary endpoint.

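### The primary endpoint is a monthly recruitment rate, but it is judged only by eye and by cuts set at its own expected values, with no measure of precision

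*Combined protocol and SAP*

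**What the plan says.** Section 9.1 states the endpoint as a rate: "This is a pilot-feasibility study with the primary endpoint of enrollment per month over a 36-month period". It chose the 36-month period because there were no earlier feasibility data, and it says the results will feed the planning of a post-pilot study.

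Section 2.2.1 defines success by the rate alone: "Reaching the target recruitment rate of one patient every 6 weeks over a 36-month period will be regarded as successful". Section 7.1 says the same. Section 9.2.2 converts the rate to a count, "one participant every 6 weeks over a 36-month period (target n=26", and adds an expectation on data quality, "We estimate a total of 85% of patients with complete data", and a second target: "We will regard a total of 22 patients as a target in meeting the primary endpoint". The synopsis, under Statistical Methods, joins the two counts in one rule: "Recruitment of ≥ 26 participants and study completion and complete data on ≥ 22 patients will be a success regarding the primary endpoint".

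For the analysis itself, section 9.2.2 says only "Study recruitment will be plotted over time and actual and target recruitment will be visually compared". The synopsis describes the same visual comparison by month. No confidence interval, other measure of precision or intermediate zone is given for recruitment or completeness anywhere in the document, and no probability of meeting the cuts is stated.

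**The concern.** The study is run to learn a recruitment rate for later planning. A plot judged by eye and a yes/no result do not show how well that rate has been determined. At counts in the twenties the uncertainty is large, and a planner who is told only that the target was met cannot see it.

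The cuts also appear to have no margin below expectation. A threshold placed at the expected value is missed by chance in a sizeable share of studies whose underlying rate is exactly as planned. One patient more or fewer can then reverse the stated primary result while the evidence about the rate hardly changes.

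**Working it through.** **Inputs.** Target of one participant per 6 weeks for 36 months, with n = 26 (section 9.2.2). Completeness of 85% (9.2.2). Enrolment of 90%, with no denominator stated (9.2.2). Cuts of at least 26 recruited and at least 22 complete (synopsis).

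**1. Reproducing the plan's targets.** 36 months is 156 weeks, or 156.5 by calendar days. 156/6 = 26.0 and 156.5/6 = 26.1; the plan says 26. 26 x 0.85 = 22.1; the plan says 22. Both figures reproduce, and both cuts therefore equal their expected values.

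**2. Chance of meeting the cuts when the true rate equals the target.** The plan gives no accrual model. Assume N recruited ~ Poisson(m) and, given N, completers C ~ Binomial(N, 0.85), with no cap on enrolment.

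| Rule | m = 26.0 | m = 26.1 |
|---|---|---|
| P(N ≥ 26), recruitment alone (2.2.1, 7.1) | 0.526 | 0.533 |
| P(C ≥ 22), completers alone | 0.537 | 0.543 |
| P(N ≥ 26 and C ≥ 22), synopsis | 0.469 | 0.476 |

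The joint figure is the sum over n ≥ 26 of P(N = n) x P(Bin(n, 0.85) ≥ 22).

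**3. Exactly 26 enrolled.** The recruitment cut is then met by definition. P(Bin(26, 0.85) ≥ 22) = 0.650, so the joint rule is missed 35% of the time.

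**4. Recruitment from a list.** Assume a fixed number M is approached (the plan gives none) and that the 90% is uptake among them, so N ~ Binomial(M, 0.90), with completeness as before.

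| M approached (assumed) | Expected N | P(N ≥ 26) | P(both cuts met) |
|---|---|---|---|
| 29 | 26.1 | 67% | 52% |
| 30 | 27.0 | 82% | 68% |
| 31 | 27.9 | 92% | 80% |

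**5. What the data would say about the rate.** Exact Poisson 95% limits for a count k are χ²(0.025; 2k)/2 and χ²(0.975; 2k+2)/2, divided by 36 months.

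| Recruited | Limits for the count | Rate per month (95% CI) | Recruitment cut |
|---|---|---|---|
| 25 | 16.2 to 36.9 | 0.69 (0.45-1.03) | missed |
| 26 | 17.0 to 38.1 | 0.72 (0.47-1.06) | met |

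For 26 recruits the interval runs from one patient per 156/38.1 = 4.1 weeks to one per 156/17.0 = 9.2 weeks. For 22 of 26 complete, the proportion is 85% with an exact binomial 95% CI of 65% to 96%.

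**The case against.** The strongest reply is that this is a descriptive single-centre pilot. A target set at the hoped-for rate is an ordinary benchmark, a count over a fixed 36 months already gives a rate, and an interval could be added at reporting. Much of this stands. The absence of a formal test is not an error, the point estimate follows directly from the count, and no result becomes invalid. What remains is that the plan specifies no measure of precision for its own primary endpoint.

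A second reply concerns the model, and it also stands. Section 4.1 describes searching records back to 2012, reviewing clinic schedules and telephoning patients, which is not passive arrival. A team working from a list can approach one or two more people, and step 4 of the working shows how much that raises the chance of success.

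Three stronger readings are tempting, and the documents do not support them:

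- A reader might infer that the primary result is a coin toss whenever the planning assumptions hold. Poisson accrual is not one of the plan's assumptions, and the 90% enrolment that it does assume leads to other figures.
- A reader might infer that a site enrolling exactly 26 fails half the time. It meets the recruitment cut with certainty and misses the completeness cut 35% of the time.
- A reader might infer that missing 26/22 rules out the post-pilot study, or that a test against a lower minimum rate is needed. The cuts define success on the primary endpoint only. No section makes them a go/no-go rule, and no minimum rate is stated.

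**Conclusion.** The point holds as a gap in precision and as a cut without margin. The primary endpoint is a rate meant to inform later planning, yet it is assessed only by visual comparison and by thresholds equal to their expected values.

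If the true rate equals the target, accrual is Poisson and completeness is 85%, about 53% of such studies reach 26 and 47-48% meet both cuts. These probabilities depend on the model and on how the target is read, so they illustrate the problem and are not a fixed property of the plan. The intervals in step 5 make the point without a forecast of success, though the rate interval still treats the count as Poisson: 25 and 26 recruits carry nearly the same information and receive opposite results on recruitment, and a result reported as success at 26 is compatible with one patient per 9.2 weeks. The remedy is a worthwhile and almost free improvement; its absence would not invalidate the study.

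**What to change.** In section 9.2.2 and in the synopsis, make the primary analysis:

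- the recruitment rate per month over the 36 months, with its exact Poisson 95% CI; and
- the proportion of recruited participants with complete data, with its exact binomial 95% CI.

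Keep the plot and the 26 and 22 targets as benchmarks reported alongside these estimates. State that post-pilot accrual planning will draw on the estimate and its interval, and leave the choice of planning rate within the interval to those designing that study.

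The cost is a few sentences of wording and two exact intervals, with no additional patients, visits or data. The downside is that a count of 26 would be reported with a wide interval and not as an unqualified success.
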